6.5 ASSESSMENT OF ENDPOINTS

A. Safety monitoring post-gene transfer

Monitoring will occur on Study Days 1, 7, 14, 30, 45, 60, 90,180, and continue at 9, 12, 18, and 24 months post gene transfer. The following parameters will be included at different time points during the monitoring evaluations (see study timeline section 6.7):

- Physical Exam
- ALT
- AST
- GGT
- Total bilirubin
- Glucose
- PT/PTT
- CBC/Diff/Platelet with smear
- Serum Creatine kinase (CK)
- Creatinine/BUN
- Cystatin C
- Alkaline phosphatase
- Amylase
- Total Protein
- Urinalysis
- Blood antibody to AAV1 and follistatin
- ELISPOT assay to detect T cell response to AAV1 capsid proteins and follistatin
- Blood circulating follistatin
- Photograph of injection site/ surrounding area
- Adverse events
- Pulmonary Function Test (PFT)

B. Efficacy Monitoring

I. Primary Outcome

Safety is a primary outcome for this clinical gene transfer trial.

II. Secondary Outcomes:

- The distance walked on the 6MWT is the primary functional outcome to be evaluated. Time to walk and run, strength test, functional test, and reaching ability will be included in PT testing. Functional testing will be performed at baseline and at days 30, 60, 90,180, and 9, 12, 18 and 24 months post-gene transfer.
- Life quality questionnaire will be completed at baseline and 6, 12, 18 and 24 months post-gene transfer.
- In order to maximize potential benefit of follistatin gene therapy, subject will be instructed to continue strengthening exercise at home at least 3 times per week as instructed by physical therapists (PT), and asked to report the frequency of exercise. The subjects who follow the exercise instruction will be incentivized by video display and offered \$10 per week if they fill out their log showing bike riding complete.
- MRI studies of leg muscles will be done pre and post gene transfer (6, 12 and 24 months) to study muscle size, fibrosis and fat content.
- EIM measurement will quantify the pathological status of muscles.
- Muscle biopsies on quadriceps muscles (a muscle biopsy on one leg at baseline screening visit and the post gene transfer biopsy on the opposite leg at day 180), will include general histological evaluation. Assessment will consist of morphometric analyses for quantification of fiber size, fibrosis, inflammatory process, satellite cells and regeneration. Muscle tissue obtained at biopsy will also be assessed for viral DNA (qPCR), and follistatin transgene expression

6.6 STATISTICAL ANALYSIS

This is a phase I/IIA trial, with safety as the primary measure. For each measure based on differences between pre- and post-gene transfer examinations (clinical) analyses will be based on a paired t test, with a p value of < 0.05 indicating significance.

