1.0 PROTOCOL SYNOPSIS

Title	Phase I/IIa Clinical intramuscular gene transfer of rAAV1.CMV.huFollistatin344 trial to							
	patients with Duchenne muscular dystrophy.							
Study Number	N = 6 DMD boys							
Clinical Study Phase	Phase I/IIa trial							
Number of Centers	Single site (Nationwide Children's Hospital)							
Study Objectives	Safety and increase distance in 6 MWT							
Study Design	rAAV1.CMV.huFollistatin344 injections to gluteus muscles, quadriceps, tibialis anterior							
Patient Population	Inclusion Criteria							
	1. Age 7 or older							
	2. Confirmed DMD gene mutations							
	3. Impaired muscle function based on clinical evidence including difficulty							
	climbing stairs, getting from the floor (Gowers' sign), and weakness of							
	individual muscles of extremities							
	4. Males of any ethnic group will be eligible							
	5. Ability to cooperate with study procedures including muscle testing.							
	6. Willingness of sexually active subjects with reproductive capacity to practice							
	reliable method of contraception							
	7. Subjects must be on stable dose of prednisone or deflazacort for three months at							
	time of enrollment. Subjects will continue the steroid dose post gene transfer as							
	part of the standard of care for DMD patients. Dose adjustment could be							
	considered if there are adverse effects.							
	Exclusion Criteria							
	8. Active viral infection based on clinical observations.							
	9. The presence of a DMD gene mutation without weakness or loss of function							
	10. Symptoms or signs of cardiomyopathy, including:							
	• Dyspnea on exertion, pedal edema, shortness of breath upon lying flat,							
	or rales at the base of the lungs \sim Echocardiogram with ejection fraction below 40%							
	• Echocardiogram with ejection fraction below 40%							
	11. Serological evidence of HIV infection, or Hepatitis A, B or C infection							
	12. Diagnosis of (or ongoing treatment for) an autoimmune disease							
	13. Concomitant illness or requirement for chronic drug treatment that in the opinion							
	of the PI creates unnecessary risks for gene transfer							
	14. Subjects with rAAV1 binding antibody titers > 1:50 as determined by ELISA							
	immunoassay 15. Abnormal laboratory values for liver, kidney, CBC, in the clinically significant							
	range, based upon normal values in the Nationwide Children's Hospital							
	Laboratory							

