Study Procedures	The vector will be delivered to both limbs via multiple, direct intramuscular injections of							
Staty 110ccuircs	rAAV1.CMV.huFollistin344; the number of injections per muscle will depend on the size							
	of the patient. A total dose of 2.4 X 10^{12} vg/kg (1.2 X 10^{12} vg/kg/limb) will be delivered							
	to the lower limbs of 6 DMD subjects.							
	Patients will also receive conscious sedation by an anesthesiologist at Nationwide							
	Children's Hospital for the injections.							
Primary Outcome	Safety is a primary outcome for this clinical gene transfer trial.							
I i mary Gutcome	_ savet, is a primary outcome for and eminear Bene dansfer dual.							

Secondary Outcomes	 The distance walked on the 6MWT is the major functional outcome to be evaluated. Other tests include time to walk and run, strength test, functional test, and reaching ability. MRI studies of leg muscles will be done pre and post treatment (6, 12 and 24 months) to study muscle size, fibrosis and fat content. EIM measurement will quantify the pathological status of muscles. Muscle biopsies on quadriceps muscles (a muscle biopsy on one leg at baseline screening visit and the post gene transfer biopsy on the opposite leg at day 180), will include general histological evaluation. Assessment will consist of morphometric analyses for quantification of fiber size, fibrosis, inflammatory process, satellite cells and regeneration. Muscle tissue obtained at biopsy will also be assessed for viral DNA (qPCR), and follistatin transgene expression.
Study Duration	We will evaluate short-term safety over a two year period. Subjects will be tested at baseline and return for follow up visits on days 7, 14, 30, 45, 60, 90, 180, and 9, 12, 18 and 24 months post-gene transfer.
Sample Size	Six DMD patients will receive rAAV1.CMV.huFollistatin344 to both limbs by multiple injections to gluteal muscles, quadriceps and tibialis anterior muscles.
Statistical Analysis	This is a phase I/IIA trial, with safety as the primary measure. For each measure based on differences between pre- and post-gene transfer examinations (clinical) evaluated by paired t test, with a p value of < 0.05 indicating significance.

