4.2 SECONDARY OBJECTIVE

Efficacy measures will be used as secondary outcomes and include the distance walked on the 6MWT, functional tests by PT, life quality questionnaire, MRI, EIM, and muscle biopsy. Subject will have follow up visits on days 7, 14, 30, 45, 60, 90, 180 and 9, 12, 18 and 24 months post-gene transfer.

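### Section 6.6 calls p < 0.05 significant for every measure and does not carry the 6MWT's lead status into the testing rule

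*Combined protocol and SAP*

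**What the plan says.** Section 6.6 is the whole statistical plan. After stating that safety is the primary measure, it says: "For each measure based on differences between pre- and post-gene transfer examinations (clinical) analyses will be based on a paired t test". The same sentence then fixes one threshold for all of these tests: "with a p value of < 0.05 indicating significance". The synopsis repeats this. Neither place gives a multiplicity adjustment, a testing order, an analysis visit or an exploratory label.

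The ranking of outcomes is given elsewhere:

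- Section 4.1 makes safety the primary objective.
- Section 4.2 makes efficacy secondary: "Efficacy measures will be used as secondary outcomes and include the distance walked on the 6MWT, functional tests by PT, life quality questionnaire", followed by MRI, EIM and muscle biopsy.
- Section 6.5 B singles out one efficacy measure: "The distance walked on the 6MWT is the primary functional outcome to be evaluated". The synopsis gives the 6MWT equivalent standing among the secondary outcomes and adds: "Other tests include time to walk and run, strength test, functional test, and reaching ability".
- The synopsis objective line reads "Safety and increase distance in 6 MWT". It places the walk test beside safety without saying that one is primary and the other secondary.

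**The concern.** Sections 6.5 and 6.6 do not connect. Section 6.5 says which efficacy measure leads. Section 6.6 then gives every measure the same threshold and the same word, significance. Applied literally, p = 0.04 on reaching ability is described exactly as p = 0.04 on the 6MWT would be.

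This point is about the family of different endpoints at one visit. Repeated visits of a single endpoint matter here only because the fix must not leave them open.

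What is at stake is the wording of the efficacy conclusion from an uncontrolled study of six boys. The protocol itself shows that such results carry weight: walking gains in a six-patient Becker trial are the rationale for this one (section 5.0), support its dose selection (section 7.2) and are cited as a possible benefit to participants (section 11.4). A flat 6MWT beside one nominally significant strength result would leave the report without a pre-stated rule for which of the two speaks for efficacy.

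**Working it through.** The documents contain no family-wise error, power or sample-size calculation, so there is no figure of the plan's own to reproduce.

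**Inputs from the documents**

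- Level per test: 0.05 (section 6.6). Sidedness is not stated; two-sided is assumed.
- Test: paired t on change scores. With n = 6 ("Six DMD patients will receive rAAV1.CMV.huFollistatin344 to both limbs") and complete data there are 5 degrees of freedom and the critical value is 2.571.
- PT measures: 6MWT, time to walk and run, strength, functional test, reaching ability = 5. Some are categories with unlisted components, so 5 may be low.
- Other measures named in section 6.5: quality of life 1 (if a single score), MRI size, fibrosis and fat 3, EIM 1, biopsy fiber size, fibrosis, inflammation, satellite cells and regeneration 5. Total 5 + 1 + 3 + 1 + 5 = 15.

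**Where the measures coincide (section 6.7 timeline)**

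| Visit | Measures |
|---|---|
| Days 30 and 60, 9 months | 5 |
| Day 90 (PT, EIM) | 6 |
| Day 180 (all) | 15 |
| 12 months (PT, quality of life, MRI, EIM) | 10 |
| 18 months (PT, quality of life) | 6 |
| 24 months (PT, quality of life, MRI) | 9 |

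**Assumptions not in the documents**

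No true mean change, normal change scores, and equal correlation between measures. The correlation is unknown and is varied from 0 to 0.9.

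**Independent measures (closed form)**

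- Any p < 0.05: 1 − 0.95^5 = 0.226 and 1 − 0.95^15 = 0.537.
- Any false gain, at 0.025 in the favourable direction: 1 − 0.975^5 = 0.119 and 1 − 0.975^15 = 0.316.

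**Correlated measures**

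Simulation of 200,000 trials per setting, six boys each, with change = √ρ × shared term + √(1 − ρ) × own term, and a two-sided paired t test at 0.05 on each measure:

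| Correlation ρ | 5 measures, any | 5 measures, gain only | 15 measures, any | 15 measures, gain only |
|---|---|---|---|---|
| 0 | 0.23 | 0.12 | 0.54 | 0.32 |
| 0.5 | 0.20 | 0.10 | 0.41 | 0.21 |
| 0.8 | 0.14 | 0.07 | 0.24 | 0.12 |
| 0.9 | 0.11 | 0.06 | 0.17 | 0.09 |

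A single test would give 0.05 for any result and 0.025 for a false gain. For five measures the ratio to 0.05 is 0.20/0.05 = 4 at correlation 0.5, and 0.115/0.05 = 2.3 at correlation 0.9 (unrounded rate 0.115).

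**A check that bears on the fix**

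Section 6.5 schedules the 6MWT at eight post-treatment visits. The same simulation with eight correlated tests gives 0.18 at correlation 0.8 and 0.28 at correlation 0.5. Restricting the claim to the 6MWT therefore holds 5% only if one visit is named.

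**The case against.** The strongest reply is that the plan already ranks its outcomes: safety is primary, efficacy is secondary, and the 6MWT leads the functional measures. Section 6.6 follows directly after that ranking and can be read as defining a nominal test, not as saying which result counts as efficacy. In a six-boy phase I/IIa trial, formal control across secondary outcomes is also largely a matter of preference. Halting rests on adverse-event grade and relatedness (sections 7.3, 7.4 and 12.1), and nothing depends on an efficacy p value.

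Much of this stands, and it limits what can be claimed. Three stronger readings are tempting but not supported.

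- A reader might infer that the plan has no hierarchy. It has one; the testing rule simply does not use it.
- A reader might take 41% as the error rate at any visit. All 15 measures coincide only at day 180. Section 6.6 also limits its rule to clinical examinations, and that word may exclude MRI, EIM and biopsy, which supply 9 of the 15. In addition, 41% holds only at the assumed correlation of 0.5.
- A reader might conclude that a false efficacy finding is likely. The any-result figures include significant worsening, which nobody would report as benefit. The false-gain figures at correlation 0.5 are 10% and 21%. Section 5.0 describes the disease as steadily progressive, so no mean change is itself a simplification; with a true mean decline, false gains would be rarer.

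The reply does not answer the remaining point. An early-phase, safety-first design is a reason to label the efficacy measures exploratory. Section 6.6 instead attaches significance to each one.

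**Conclusion.** The point holds in a limited form: the per-measure rule in section 6.6 and the synopsis is not tied to the 6MWT's lead status, and no other measure is marked exploratory.

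The main figure is the five-measure one, because those measures fall within any reading of the word clinical. The 15-measure figure applies at day 180 only, and only on the broad reading. Both rest on six complete boys, no true mean change and an equal correlation that the documents do not supply. The direction does not depend on that choice: the rate exceeds 5% at every correlation tried.

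This is a cheap improvement of modest severity. It affects how secondary efficacy may be described, not safety monitoring or trial continuation.

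**What to change.** Replace the per-measure sentence in section 6.6 and in the synopsis with text along these lines:

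> The change in 6MWT distance from baseline to [one named visit, for example 12 months] is the only efficacy comparison for which p < 0.05 will be described as statistically significant. The 6MWT at other visits and all other PT, quality of life, MRI, EIM and biopsy measures are exploratory. They will be reported as individual values and mean change with 95% confidence intervals, without a claim of significance.

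The visit must be chosen before any post-treatment efficacy data are reviewed. The synopsis objective line should also be aligned with sections 4.1 and 4.2: safety primary, 6MWT the lead secondary outcome.

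The cost is a few sentences, with no added patients, data or procedures, and the 6MWT test keeps its full 0.05. A Bonferroni split would instead need 0.05/5 = 0.01 or 0.05/15 = 0.0033 per test. The downside of the proposed text is that no other measure or visit can be called significant in the report.

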6.7 STUDY TIMELINE

STUDY TIMELINE																
Study Interval	Baseline Screening	In	/ecto jection patie	on	Follow Up (Outpatient)											
Visit	1	2			3	4	5	6	7	8	9	10	11	12	13	14
Days in Study	-45 to -1	-1	0	1	7	14	30	45	60	90	180	194*	9 mo	1 yr	18 mo	2 yr
Informed Consent	x															
Medical History	Х															
Physical Exam & vitals	x	x		x	x	х	х	х	х	x	x	х	х	х	х	x
ECHO/EKG	x															
Chest X-Ray	х															
MRI	х										х			Х		х
Hepatitis A, B & C HIV	x															
Safety labs	Х			Х	Χ	Х	Х	Х	Х	Х	Х					
Urinalysis	x			х	х	х	х	х	х	х	х					
Pulmonary function test	x						х			x	x		х	х		
PT evaluation	x						х		х	х	х		х	х	х	х
Life quality questionnaire	x										x			х	х	x
EIM	х									х	х			Х		
Immunology studies	x				x	x	х	х	x	x	x		x	x	x	x
Circulating follistatin	x						x			x	x		x	x	x	x
Gene Transfer			х													
Muscle Biopsy	x										х					
Photograph of injection site			x	x	x	x	х	x	x	x	x	x	х	x	x	x
Adverse Events			х	х	х	Х	Х	Х	х	х	х	х	Х	х	х	х
Concomitant Medications	To be collected from time of consent until final study visit, recorded on separate CRF															

Note: There will be a flexibility of a +/-7 working days for each of the planned study visits including screening to adjust the schedule to any unanticipated event. There will also be potential additions to care based on best medical management if the need arises including additional fluids to restore blood volume.

*: The follow up post-biopsy visit scheduled 2 weeks post-biopsy is made optional to give subjects the choice to have the stiches removed at their local doctor's office.

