6.4.2 FOLLOW UP

Subjects will return for follow up visits on days 7, 14, 30, 45, 60, 90,180, and 9, 12, 18, and 24 months post-gene transfer. Toxicity monitoring on each of these dates (including day 1 post-gene transfer) are described in the following sections of the protocol.

We will follow the most recent FDA guidelines with regard to long-term patient follow up following gene transfer. Our proposed vector has a very low probability of gene transfer-related delayed adverse events. We will, however, evaluate short-term safety over a two-year period that incorporates the active phase of the protocol (see assessment of endpoints below). If newly

identified risks are associated with our product, or if the patients suffer any adverse events during this period, we will initiate a long-term follow-up according to the FDA guidelines.

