7.3 DOSE LIMITING TOXICITY

In reporting adverse events we will follow the final regulations issued by the Food and Drug Administration addressing the safety reporting requirements for investigational new drug applications (INDs) found in 21 CFR part 312 and for bioavailability and bioequivalence studies found in 21 CFR part 320. "Safety Reporting Requirements for INDs and BA/BE Studies".

The classification for adverse events to be used is the following:

- 1 Mild adverse event; did not require treatment
- 2 Moderate adverse event; resolved with treatment
- 3 Severe adverse event; inability to carry on normal activities; required professional medical attention
- 4 Life-threatening or permanently disabling adverse event
- 5 Fatal adverse event In this grading system, "severe" is not equivalent to *seriousness*.

The definitions to be employed will follow the final regulations issued by the FDA in September 2010 "Safety Reporting Requirements for INDs and BA/BE Studies.

Dose limiting toxicity (DLT) is defined as any adverse event that is possibly, probably, or definitely related to the study agent. This would include any grade 3 according to the classification given above. Study enrollment will be halted by the investigators when any subject experiences a Grade 3, or higher adverse event toxicity that is possibly, probably, or definitely related to the study drug.

Laboratory tests with values within the clinically significant range will be repeated during the same visit whenever possible. If the test result returns after the subject leaves the clinic, they will be immediately contacted. For local residents they will be asked to return to the outpatient clinic for a repeat test. For non-local residents, arrangements will be made to have the blood test redrawn in a laboratory close to home or by their primary care physician. To avoid any confusion for the primary care physician, they will be informed (with permission from the subject) of their participation in the study at the time of gene transfer. If the AE requires treatment, this will be carried out by the primary care physician or a doctor of choice selected by the subject. We will obtain copies of repeat laboratory tests and any relevant medical records that will be added to the subject's research chart.

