Only those adverse events requiring treatment will qualify as DLT. The PI will fulfill the reporting responsibilities under 21 CFR 312.32(c), to notify FDA in an IND safety report of potentially serious risks, as soon as possible, but no later than 15 calendar days after the

investigator receives the safety information and determines that the information qualifies for reporting. The investigator will confer with the DSMB, IRB, IBCSC, CBER, FDA, OBA, and NIH before continuing enrollment.

Test	Units	Reference Range		Clinically Significan Range		
Hemoglobin	g/dL	2Y - 5Y	11.5 - 13.5	< 8.0 or > 18		
0	-	6Y - 11Y	11.5 - 15.5			
		12Y – Adult	12.0 - 16.0			
WBC	K/cu mm	4Y - 5Y	5.5 - 15.5	$\leq 3.5 \text{ or} \geq 20$		
		6Y - 9Y	5.0 - 14.5			
		10Y - 20Y	4.5 - 13.5			
		21Y – Adult	4.5 - 11.0			
BUN	mg/dL	5 - 18		≥35		
РТ	sec	12.4 - 14.7		\leq 5.0 or \geq 35.0		
PTT	sec	24 - 36		≥ 125		
Platelet	K/cu mm	140 - 440		\leq 90 or \geq 800		
Amylase	U/L	0 - 17Y	<110	\geq 200		
		18Y – Adult	30 - 110			
Total Protein	g/dL	3Y - 15Y	5.8 - 8.7	$\leq 4.4 \text{ or} \geq 9.5$		
		16Y – Adult	6.4 - 8.4			
Total Bilirubin	mg/dL	0.1 – 1.0 mg/dL		≥ 3.0		
Creatinine	mg/dL	4Y - 7Y	0.3 - 0.8	≥ 1.8		
	Ū.	8Y - 10Y	0.3 - 0.9			
		11Y - 12Y	0.4 - 1.0			
		13Y - 17Y	0.5 - 1.2			
		18Y – Adult	0.6 - 1.3			
GGT*	U/L	8 - 78		3XULN		
ULN= upper limit r	normal					

Table of Clinically Significant Laboratory Ranges

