7.4 STOPPING AND DISCONTINUATION RULES

An independent Data Safety Monitoring Board (DSMB) will be established by the sponsoring agency including a safety monitor for the study. Safety data will be monitored on a continual basis throughout the trial. The DSMB can recommend early termination of the trial for reasons of safety. Study enrollment will be halted by the investigators when any subject experiences a Grade 3, or higher adverse event toxicity that is possibly, probably, or definitely related to the study drug. This will include:

Grade 3 Severe or medically significant but not immediately life-threatening; hospitalization or prolongation of hospitalization indicated; disabling; limiting self care ADL**.

Grade 4 Life-threatening consequences; urgent intervention indicated.

Grade 5 Death related to AE.

Activities of Daily Living (ADL)

*Instrumental ADL refer to preparing meals, shopping for groceries or clothes, using the

telephone, managing money, etc.

**Self care ADL refer to bathing, dressing and undressing, feeding self, using the toilet, taking

medications, and not bedridden.

If after review by the DSMB, IRB, IBCSC, NIH-OBA and FDA, the decision is made to continue according to this study protocol.

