8.0 ADVERSE EVENT MONITORING AND REPORTING

8.1 DEFINITION OF AN ADVERSE EVENT

As stated above this protocol will follow the final regulations issued by the Food and Drug Administration addressing the safety reporting requirements for investigational new drug applications (INDs) found in 21 CFR part 312 and for bioavailability and bioequivalence studies found in 21 CFR part 320. "Safety Reporting Requirements for INDs and BA/BE Studies".

http://www.fda.gov/downloads/Drugs/GuidanceComplianceRegulatoryInformation/Guidances/U CM227351.pdf

Adverse Events will be collected throughout the study from enrollment to last follow up visit.

Adverse Event (AE): Adverse event means any untoward medical occurrence associated with the use of a drug in humans, whether or not considered drug related.

Adverse events will be graded by the investigator accordingly:

Grade 1 Mild; asymptomatic or mild symptoms; clinical or diagnostic observations only; intervention not indicated.

Grade 2 Moderate; minimal, local or noninvasive intervention indicated; limiting age-appropriate instrumental ADL*.

Grade 3 Severe or medically significant but not immediately life-threatening; hospitalization or prolongation of hospitalization indicated; disabling; limiting self care ADL**.

Grade 4 Life-threatening consequences; urgent intervention indicated.

Grade 5 Death related to AE.

A Semi-colon indicates 'or' within the description of the grade.

A single dash (-) indicates a grade is not available.

Activities of Daily Living (ADL)

*Instrumental ADL refer to preparing meals, shopping for groceries or clothes, using the

telephone, managing money, etc.

**Self care ADL refer to bathing, dressing and undressing, feeding self, using the toilet, taking

medications, and not bedridden.

Association or relatedness to the study agent, study procedures and the subject's pre-existing disease will be graded as follows: 5 = unrelated, 4 = unlikely, 3 = possibly, 2 = probably, and 1 = definitely related.

Adverse reaction: An adverse reaction means any adverse event caused by a drug. Adverse reactions are a subset of all suspected adverse reactions for which there is reason to conclude that the drug caused the event.

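### The ±7 working-day window is wider than the 7 days between the first two outpatient safety visits, so the first labs after day 1 can fall on day 14, or on day 16 or 18, within protocol

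*Combined protocol and SAP*

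**What the plan says.** Section 6.4.2 sets the outpatient schedule: "Subjects will return for follow up visits on days 7, 14, 30, 45, 60" and onward to 24 months. Section 6.5 A repeats it for safety, adding the inpatient day: "Monitoring will occur on Study Days 1, 7, 14, 30, 45, 60" and later. In the section 6.7 table, safety labs are marked on day 1, then days 7 and 14, then from day 30. The first immunology sample after transfer is on day 7. Nothing is scheduled between day 1 and day 7.

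The note under that table applies one tolerance to everything: "flexibility of a +/-7 working days for each of the planned study visits including screening to adjust the schedule to any unanticipated event". I found no narrower early window, minimum spacing or order rule elsewhere.

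Section 7.3 says what follows an abnormal result: "Laboratory tests with values within the clinically significant range will be repeated during the same visit whenever possible". If the result comes back after the boy has left, he is contacted for a repeat test and treated if needed.

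**The concern.** A visit window should be narrower than the spacing of the visits it governs. Otherwise the schedule no longer guarantees two separate looks. As the note is written, the day 7 and day 14 visits could be merged, reversed or both pushed late, with every visit still in window.

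The main person affected is the boy already dosed. Adverse event collection and contact with the primary care physician (section 9.1) pick up symptoms. A chemistry or hematology abnormality without symptoms is seen only when blood is drawn, and the repeat-and-treat steps of section 7.3 start from that draw. All six boys receive 2.4 x 10^12 vg/kg, twice the highest total dose in the Becker trial (section 7.2).

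The consequence has limits:

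- The enrollment halt in section 7.4 ("Study enrollment will be halted by the investigators when any subject experiences a Grade 3, or higher adverse event toxicity") also requires the event to be at least possibly related to the study drug. A finding without symptoms that needs no intervention is Grade 1 under section 8.1 ("Mild; asymptomatic or mild symptoms; clinical or diagnostic observations only; intervention not indicated").
- A halt protects only boys not yet dosed. No minimum interval between boys is stated, so I do not claim that a late draw would change a later dosing.
- Antibody and ELISPOT samples would also be late. They are not in the section 7.3 "Table of Clinically Significant Laboratory Ranges", and no route from them to a halt is stated.

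**Working it through.** The protocol gives no derived figure to reproduce here. The check is calendar arithmetic.

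**Inputs.** The window is ±7 working days (section 6.7 note). The nominal visits are days 1, 7, 14, 30, 45, 60 and 90 (sections 6.5 A and 6.7). Day 1 labs are treated as fixed, because the boy is an inpatient until then (section 6.4.1). Assumptions: working days are Monday to Friday, there are no holidays, and transfer is on a weekday.

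**Step 1: width.** Seven working days forward is 9 calendar days from a Monday, Tuesday or Wednesday and 11 from a Thursday or Friday. Backward it is 11 from a Monday or Tuesday and 9 from the other weekdays. Either value exceeds 7.

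**Step 2: windows.** Days 7 and 14 fall on the same weekday as the transfer, so no weekend rule is needed. Shared days are counted inclusively from the opening of the day 14 window to the close of the day 7 window.

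| Transfer day | Day 7 window | Day 14 window | Shared days |
|---|---|---|---|
| Mon | -4 to 16 | 3 to 23 | 16 - 3 + 1 = 14 |
| Tue | -4 to 16 | 3 to 23 | 14 |
| Wed | -2 to 16 | 5 to 23 | 16 - 5 + 1 = 12 |
| Thu | -2 to 18 | 5 to 25 | 18 - 5 + 1 = 14 |
| Fri | -2 to 18 | 5 to 25 | 14 |

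**Step 3: first labs after day 1.** This is the earlier of the two actual visits.

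- Planned: day 7, gap 7 - 1 = 6 days.
- Only the day 7 visit slips, to day 14 or later, with the day 14 visit on time: day 14, gap 14 - 1 = 13 days.
- Both slip to the limit: day 16 (Mon to Wed transfer) or day 18 (Thu or Fri), gap 16 - 1 = 15 or 18 - 1 = 17 days.

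**Step 4: longest in-window gap between the two visits' labs.** Put the day 7 visit on the first weekday after day 1 and the day 14 visit at its late limit. Monday to Wednesday transfer gives 23 - 2 = 21 days. Thursday gives 25 - 4 = 21. Friday gives 25 - 3 = 22. The plan is 7.

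**Step 5: later visits.** The day 30 window opens on day 20 or 21 and overlaps the day 14 window by 3 to 6 days. Days 30 and 45 share 4 to 6 days, days 45 and 60 share 6, and days 60 and 90 share none. Where a nominal day is on a weekend, the late limit is counted from the Friday before and the early limit from the Monday after, which is the narrowest reading.

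**Step 6: with day 7 ±2 and day 14 ±3 (days 5 to 9 and 11 to 17).** The first labs after day 1 fall on day 9 at the latest, gap 9 - 1 = 8 days. The longest gap between the two visits, weekdays only, is 10, 11, 11, 10 and 12 days for Monday to Friday transfers. The day 7 window keeps 3, 4, 5, 4 and 3 weekdays, and the day 14 window keeps 5 in every case. The day 14 window closes on day 17, before day 30 opens.

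**The case against.** The strongest reply is that the planned schedule is sound and the note is only for unanticipated events. That is true. The day 16 or 18 result needs two late visits in the same boy, and the 21 to 22 day gap needs one visit early and the other at its limit. Nothing in the documents suggests that either is likely.

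The one-slip case can also be disputed. The timeline numbers these visits 3 and 4. If that is read as a fixed order on separate days, with day 14 on time, the latest weekday for the day 7 visit is day 11 (Monday transfer) or day 13 (Tuesday to Friday). The gap is then 10 or 12 days rather than 13, still about twice the planned 6. The both-slip result does not change, because the day 14 visit can still follow.

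There are partial safeguards. The note allows extra care if the need arises, the DSMB meets after the first boy's day 30 visit, and its reports include a visit timeline for each participant (section 12.1). These would reveal a long gap afterwards but would not bring forward the draw that finds a silent abnormality. The Becker trial reported no safety concerns with this vector, but at half this total dose or less.

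One point stands in full. A tighter window does not itself bring in a family that cannot travel. Day 9 is the latest compliant date, not a guaranteed draw date.

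**Conclusion.** The concern holds. The tolerance exceeds the spacing of the first two outpatient safety visits for every weekday of transfer. A compliant schedule can therefore put the first labs after day 1 on day 14 (7 days later than planned), or on day 16 or 18 (9 or 11 days later). The arithmetic assumes weekday transfer and no public holidays; a holiday could add a day or more. The figures are in-window extremes, not expected timings, and the documents give no rate or timing for silent early abnormalities. This is a defective rule in a trial whose primary outcome is safety. It should be corrected, but it does not undermine the planned schedule.

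**What to change.** In the section 6.7 note, give the first two outpatient visits their own non-overlapping calendar-day windows, for example day 7 ±2 (days 5 to 9) and day 14 ±3 (days 11 to 17). The exact widths are a judgment. From day 30, keep ±7 working days and add that each visit must take place before the next one and not on the same day. Report early labs and immunology by actual day since transfer.

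The text change is two sentences, with no change to the planned visits or the analysis. The cost is less scheduling slack for families and possibly more recorded deviations, since section 13.0 allows none outside emergencies.

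To help obtain the blood on time, the local route in section 7.3 could be extended from repeat tests to routine early safety labs: "For non-local residents, arrangements will be made to have the blood test redrawn in a laboratory close to home". The documents give no such route for immunology samples, so those would still need the site visit.
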